#### Statistical Methods

SPSS 25.0 software was used for statistical analysis. Normally distributed data were expressed as mean  $\pm$  SD, and group comparisons were performed using independent samples t-test. Data with a skewed distribution were expressed as median (M) and interquartile range (IQR), and non-parametric tests were used for comparisons. Friedman's test was used for intra-group comparisons. Count data were expressed as

number (%), and comparisons between groups were performed using the  $\chi^2$  test. P<0.05 was considered statistically significant.

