### Randomization and Blinding

Using a computer-generated random sequence, a person who was not involved in the experimental operation divided the patients into two groups in which FICB was achieved with either methylene blue and ropivacaine (MB+R group) or ropivacaine only (R group). All serial numbers were encoded sequentially, kept, and scheduled for each experiment by someone other than the researcher. Because methylene blue is a blue liquid, exposure to the color could expose the experimental group. Thus, blinding was achieved by having different researchers perform different steps in the study to avoid the color affecting the experiment. The steps of the experimental procedure,

including the extraction of the liquid medicine, performance of the nerve block, and postoperative follow-up, were performed by different anesthesiologists, who were only responsible for independent experimental procedures, did not know the information about the patient outside the experiment, and did not communicate with each other about the patient and the experiment. Catheterization was not performed for any patient to prevent the color of the urine from exposing the experimental group.

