After successful nerve block, all patients were transferred to the operating room where they received routine monitoring of heart rate (HR), electrocardiogram (ECG), oxygen saturation (SpO2), etc. Radial artery puncture catheterization was performed under local anesthesia for invasive arterial pressure monitoring. For anesthesia induction, patients received an intravenous injection of propofol 1.0-2.0 mg/kg, rocuronium bromide 0.6 mg/kg, and sufentanil 0.2-0.3 µg/kg. The specifications of mechanical ventilation after endotracheal intubation were: tidal volume (VT) 6-8 ml/kg, respiratory rate (RR) 10–12 times/min, positive end expiratory pressure (PEEP) 3-5 cmH2O, and end-expiratory carbon dioxide partial pressure (PETCO2) 35~45 mmHg. Anesthesia was maintained by inhalation of 1.5%-2.0% sevoflurane along with intravenous infusion of remifentanil at 0.05-0.2 µg/kg/min and intermittent administration of rocuronium bromide 5-10 mg according to the intraoperative situation to maintain muscle relaxation. Blood pressure (BP) and HR fluctuation within 20% of baseline values was allowed according to the intraoperative situation. If BP dropped by >20% of the baseline value or if systolic BP was <90 mmHg, ephedrine 6 mg was given. If the HR was <50 beats/minute, an intravenous bolus of atropine 0.5 mg was given. All operations among included patients were performed by the same surgical team with the same surgical method, and the surgical method was hip replacement with posterolateral approach in the lateral decubitus position. The inhalation of sevoflurane and infusion of remifentanil was stopped 5 min before the end of the operation. After surgery, the patient was transferred to a recovery room, and

the endotracheal tube was removed once the patient was awake and spontaneous breathing had resumed. According to our pre-test experience, many patients refuse the use of analgesic pumps due to the relatively high cost, certain drug-related side effects, and the option of FICB. Thus, we did not include cases with post-surgical use of an analgesic pump in this study. In this study, fascia iliaca block was used to administer postoperative analgesia to patients. If the patients were not satisfied with the effect of fascia iliaca block, additional opioids were used for supplemental analgesia. At the same time, to avoid the effect of drugs on the level of patients' inflammatory factors, the use of non-steroidal analgesic drugs was prohibited.

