
### Study Outcomes

# Primary Outcomes

As a measure of pain, Visual Analog Scale (VAS) scores at both rest and with activity (passive straight leg raise at 45°) were recorded at the following time points: before block and at 2, 6, 12, 24, and 48 h postoperatively. The VAS score is a common way to assess pain using a sliding ruler about 10 cm long, marked with 10 scales on one side and "0" and "10" at each end. A score of 0 indicates no pain; a score of 10 indicates the most severe pain that is unbearable. The higher the score, the greater the degree of pain. In this study, a dedicated anesthesiologist assessed the pain of each included participant at different time points before and after surgery.

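### Pre-block VAS is collected in every participant but plays no part in the comparison of MB+R with R, which probably costs some precision on the primary outcome

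*Combined protocol and SAP*

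**What the plan says.** Under Primary Outcomes, VAS at rest and with activity is recorded "before block and at 2, 6, 12, 24, and 48 h postoperatively". The same section says that a dedicated anesthesiologist "assessed the pain of each included participant at different time points before and after surgery", so the pre-block score is meant to exist for everyone.

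Under Statistical Methods, the treatment of continuous outcomes is short:

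- Normal data: "group comparisons were performed using independent samples t-test".
- Skewed data: "non-parametric tests were used for comparisons", with no test named.
- Within groups: "Friedman's test was used for intra-group comparisons", not tied to any particular outcome.
- Significance: "P<0.05 was considered statistically significant", with sidedness not stated.

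No covariate, change score, mixed model or stratified analysis is mentioned. Randomization and Blinding says that a computer-generated sequence "divided the patients into two groups" and describes no stratification by starting pain, so the design does not use the baseline either.

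**The concern.** The trial measures the outcome variable itself before treatment and then leaves it out of the treatment comparison. If patients with more pain before the block also tend to report more pain afterwards, part of the spread in postoperative VAS is predictable from the baseline. An unadjusted test counts that part as noise, so confidence intervals are wider and power is lower than the same data could give. In the one trial actually run, the estimate also carries whatever difference in starting pain randomisation happened to leave.

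Friedman's test does not fill the gap. It asks whether scores change over time within one arm. A significant result in one arm and not in the other does not estimate MB+R versus R.

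**Working it through.** **Inputs.** The plan states no sample size, power, effect size, SD or baseline-outcome correlation, so it has no figure to reproduce. The inputs below are assumptions, apart from the 0.05 level:

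- n = 40 per arm, with 20 and 80 as a range; 1:1 allocation
- correlation r between pre-block and postoperative VAS of 0.1 to 0.5
- two-sided test at 0.05
- normal outcome with equal SDs

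**Step 1: residual variance.** A linear adjustment for one baseline leaves a fraction 1 − r² of the outcome variance.

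**Step 2: price of estimating the slope.** With one covariate, the variance of the treatment difference is inflated on average by 1 + 1/(2n − 4). At n = 40 this is 1 + 1/76 = 1.013. The net variance ratio, adjusted to unadjusted, is (1 − r²)(1 + 1/(2n − 4)).

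**Step 3: power.** By the noncentral t distribution, a standardised difference of 0.634 gives the unadjusted test 80% power at 40 per arm. Dividing the noncentrality by the square root of the net ratio, with one fewer degree of freedom, gives the last column.

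| r | 1 − r² | Net variance ratio | Change in variance | Power (80% unadjusted) |
|---|---|---|---|---|
| 0.1 | 0.99 | 1.003 | +0.3% | 79.9% |
| 0.2 | 0.96 | 0.973 | −2.7% | 81.1% |
| 0.3 | 0.91 | 0.922 | −7.8% | 83.1% |
| 0.4 | 0.84 | 0.851 | −14.9% | 85.9% |
| 0.5 | 0.75 | 0.760 | −24.0% | 89.5% |

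**Step 4: break-even.** Setting the net ratio to 1 gives r = 1/√(2n − 3):

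- 20 per arm: 1/√37 = 0.164
- 40 per arm: 1/√77 = 0.114
- 80 per arm: 1/√157 = 0.080

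Below these values adjustment costs a little. At r = 0 and 40 per arm the cost is 1.3% of variance.

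**Step 5: the same loss seen in a single trial.** The chance difference in mean baseline has standard error √(2/n) in SD units and moves the unadjusted estimate by r times that difference. At n = 40:

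- median imbalance 0.6745 × √(2/40) = 0.151 SD, so a shift of 0.015 to 0.075 SD over r = 0.1 to 0.5
- 95% limit 1.96 × √(2/40) = 0.438 SD, so a shift of 0.044 to 0.219 SD

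Over 20 to 80 per arm the median shift runs from 0.01 to 0.11 SD and the 95% limit from 0.03 to 0.31 SD. The variance of this shift is r² × 2/n, which is the share removed in Step 1. It restates the loss and does not add to it.

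**Step 6: validity of the planned test.** In 20,000 simulated null trials at 40 per arm, the unadjusted t-test rejected in 4.9% to 5.3% across r. Its level holds.

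**The case against.** The strongest reply is that this is a preference about efficiency. An unadjusted comparison of randomised groups is accepted practice and holds its level, and nothing in the plan contradicts it. That stands, and it is why the point is an improvement and not a fault in validity.

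The second reply is that the gain rests on a correlation the documents do not give. It may well be low: surgery and a block come between the two measurements, and for patients not satisfied with the block "additional opioids were used for supplemental analgesia". This also stands. At r = 0.2 the gain is about one power point at 40 per arm and half a point (80% to 80.5%) at 20 per arm. The larger gains need r of 0.4 or 0.5, for which the documents offer no support. The stakes are still uneven: over r = 0.1 to 0.5 at 40 per arm, the worst case costs 0.1 power point and the best gains 9.5.

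Third, the formulas cover the t-test branch and linear ANCOVA on normal data. VAS is bounded at 0 and 10 and may be skewed, and neither the non-parametric branch nor the mixed model is quantified. A simulation of rounded 0–10 scores with a floor at 0 (4,000 trials per setting, 40 per arm, assumed means and SDs) is reassuring. ANCOVA rejected 5.0% to 5.1% under the null, and power, unadjusted against adjusted, was 76.6% and 76.6% at r = 0.1, 75.7% and 78.7% at r = 0.3, and 75.6% and 84.7% at r = 0.5. These figures are illustrative only.

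Finally, adjustment leaves ten postoperative comparisons (five times, two conditions) with none named as decisive, and the past tense of the document suggests that data may be in hand. The first is a separate matter. The second changes the remedy but not the point.

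**Conclusion.** The concern holds. Pre-block VAS is collected in each participant, and nothing in the document gives it a role in comparing the two arms. The planned tests are valid, so what is lost is probably some precision. At an assumed 40 per arm, adjustment changes the variance of the treatment difference by anything from +0.3% to −24.0% as the correlation goes from 0.1 to 0.5. It is a net gain above a correlation of about 0.08 to 0.16, depending on whether there are 80 or 20 per arm.

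The direction is likely but the size is unknown, because sample size, allocation ratio and correlation are all assumed. The change is worth making because it is nearly free. It would not on its own make the planned results unreliable.

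**What to change.** State the role of the pre-block score in Statistical Methods:

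- Compare postoperative VAS by ANCOVA at each time point, with the pre-block VAS of the same condition (rest or activity) as covariate. Alternatively, use a mixed model over the five postoperative times with that covariate, group, time and group × time, and a stated covariance structure, for example unstructured.
- Report adjusted mean differences with 95% confidence intervals.
- If scores are skewed, use robust or bootstrap standard errors, or a rank-based ANCOVA.
- Base treatment conclusions on these between-group contrasts and keep any Friedman tests descriptive.
- Do not substitute a plain change score. With equal SDs its variance ratio is 2(1 − r), which loses precision whenever r is below 0.5.

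If outcome data have already been seen, keep the planned tests and report the adjusted analysis beside them as a labelled sensitivity analysis.

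The cost is a few lines of wording, about one degree of freedom, and slope and covariance assumptions for a bounded score. No new data are needed. The deciding time point and condition still have to be named separately.

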# Secondary Outcomes

As indicators of inflammation, the values of hypersensitive C-reactive protein

(hs-CRP), procalcitonin (PCT), and the neutrophil-to-lymphocyte ratio (NLR) also were recorded on postoperative days 1 and 2.

HR and mean arterial pressure (MAP) values were recorded at the following time points: operating room entry (T1), immediately before skin incision (T2), 1 min after skin incision (T3), skin suture (T4), and 30 min after extubation (T5). The requirement of supplemental analgesia was noted within 48 h postoperatively, along with the number of times patients got out of bed to perform activities within 48 h postoperatively and the distance walked after the patient's first attempt to get out of bed. Any occurrence of adverse reactions such as nausea, vomiting, and arrhythmia within 48 h postoperatively also was recorded. Any drug-related nerve damage after surgery was noted. Nerve deficits were defined according to sensory findings: 0—no nerve damage, 1—minor sensory paresthesia, 2—complete sensory parasthesia, 3—complete motor defect with or without sensory paresthesia, and 4—complex regional pain syndrome. Two researchers who were blinded to the group allocation assessed these outcomes.

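### The only analysis named across time points is a Friedman test inside each arm, which carries no information on methylene blue; no between-arm longitudinal analysis is named

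*Combined protocol and SAP*

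**What the plan says.** The Statistical Methods section describes two kinds of analysis.

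- **Between arms:** for normal data, "group comparisons were performed using independent samples t-test"; for skewed data, "non-parametric tests were used for comparisons", with the test not named; for counts, a chi-square test.
- **Within an arm:** "Friedman's test was used for intra-group comparisons". The outcomes and time points are not listed.

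One threshold covers everything: "P<0.05 was considered statistically significant". The within-arm results are not labelled descriptive.

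Under Primary Outcomes, VAS is scored at rest and with activity, each time "before block and at 2, 6, 12, 24, and 48 h postoperatively". That is six times under two conditions. Under Secondary Outcomes, "HR and mean arterial pressure (MAP) values were recorded at the following time points", namely T1 to T5. No repeated-measures ANOVA, mixed model, arm-by-time test or baseline-adjusted analysis is named for any of these outcomes.

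**The concern.** The trial asks whether adding methylene blue changes pain after the block. A test inside one arm asks something else: whether pain, heart rate or MAP moves between time points around an operation. It can do so with or without methylene blue.

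Two things are at stake.

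- **Misreading.** Within-arm P values judged at 0.05 can find their way into the results as if they bore on treatment, most easily as a change that is significant in one arm and not in the other. That pattern is not a test of the difference between arms.
- **Lost information.** The repeated measurements are collected, but the only method that uses them together ignores the randomisation. The between-arm methods named are single comparisons, with no overall postoperative estimate and no adjustment for the pre-block score.

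**Working it through.** **Plan's own figure.** There is none to reproduce. The documents give no sample size, power, effect size or SD.

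**Step 1. What each named method can show.**

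| Method | Compares MB+R with R | Uses several times together |
|---|---|---|
| t-test, non-parametric test, chi-square | yes | no |
| Friedman, within arm | no | yes |
| Any method doing both | none named | none named |

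That Friedman's test runs across time points is an inference from the design, because the section says only that it is for intra-group use. Repeated times are the only evident within-group comparison here.

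**Step 2. Disagreement between identical arms.** If each of two identical arms has probability p of a significant Friedman test, then

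P(exactly one significant) = 2p(1 − p).

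| p | 2p(1 − p) |
|---|---|
| 0.05 (no time effect) | 9.5% |
| 0.20 or 0.80 | 32% |
| 0.50 | 50% (maximum) |
| 0.95 | 9.5% |
| 0.99 | 2.0% |
| 0.999 | 0.2% |

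**Step 3. What time effects give those values of p.** Both arms were simulated from the same distribution and tested with the tie-corrected Friedman test. From the documents: six times and a threshold of 0.05. Assumed: VAS SD 1.2, within-patient correlation 0.5, whole-number scores, and the sample sizes shown. There were 4,000 runs per cell, so the simulation standard error is at most √(0.25/4000) = 0.8 percentage points. Entries are the percentage of trials in which exactly one arm was significant.

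| Peak-to-trough change (points) | 20 per arm | 30 per arm | 40 per arm | 60 per arm |
|---|---|---|---|---|
| 0 | 9.0 | 8.9 | 10.5 | 8.9 |
| 0.25 | 17.5 | 19.9 | 26.8 | 33.6 |
| 0.5 | 38.7 | 49.3 | 49.5 | 38.0 |
| 0.75 | 49.0 | 31.8 | 15.0 | 2.3 |
| 1.0 | 23.6 | 5.2 | 0.8 | 0.0 |
| 1.5 | 0.4 | 0.0 | 0.0 | 0.0 |

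**Step 4. Two further settings, also assumed.**

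- *Five times, as for heart rate and MAP.* With 40 per arm, correlation 0.5 and a shift at one time only, exactly one of two identical arms was significant in 28%, 45%, 49% and 31% of trials for shifts of 0.2, 0.3, 0.4 and 0.5 SD.
- *A larger change, as for rest VAS.* With a pre-block mean of 3.5, later means of 1.0 to 3.0 and SD 1.2, both arms were significant in all 500 simulated trials, at 30 and at 50 per arm.

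In the first setting disagreement is a matter of chance. In the second the test is significant in both arms whatever the treatment does. Neither result bears on methylene blue.

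**The case against.** The plan does have direct between-arm tests, and they answer the randomised question. A reader might infer that the trial cannot show an effect of methylene blue as planned. The documents do not support that, since the Friedman test is an addition to those tests and not a substitute for them.

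A reader might also infer that the sponsor will treat significance in one arm only as a treatment effect. No section says so. It is a misreading the plan leaves open, not a stated decision rule.

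Nor is disagreement between identical arms frequent in general. It is high only near 50% power per arm. For VAS from before the block to 48 h, a change of more than a point is plausible, and the rate is then close to zero except in the smallest samples. For heart rate and MAP a modest change is possible, but the documents do not settle its size. The Friedman sentence follows the one on skewed data, so it may not cover every outcome.

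One might add that Friedman's test needs complete rows and so describes different patients from the between-arm tests. With six times and independent missingness of 2%, 5% or 10% per time (assumed), the loss would be 1 − 0.98⁶ = 11.4%, 1 − 0.95⁶ = 26.5% or 1 − 0.90⁶ = 46.9%. But the exclusion criteria remove patients who cannot be followed up at the scheduled times. On the natural reading both analyses then use the same patients, so this argument is weak.

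Finally, an arm-by-time test alone would be a poor replacement. A constant difference between arms over T1 to T5 produces no interaction. By the order of events under Operative Procedures, T1 comes after the block, so heart rate and MAP have no listed pre-treatment value to adjust for. This stands, and the fix below allows for it.

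What remains is that the only analysis across time lacks a treatment contrast, is not labelled descriptive, and has no between-arm counterpart.

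**Conclusion.** The point holds in a limited form. The within-arm Friedman tests give no evidence on methylene blue, and the plan names no between-arm longitudinal analysis for VAS, heart rate or MAP. The planned between-arm tests are not invalidated.

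If the within-arm verdicts were nevertheless compared, the false one-arm pattern would appear in about 10% of trials with no time effect, in up to about 50% with a modest effect for the sample size, and almost never with a strong one. The 50% ceiling follows from the formula, given independent arms with equal p. Where a given outcome falls below it depends on the assumed sample size, SD, correlation and time profile. The plan should be changed, because the better analysis needs no new data and closes off the misreading.

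**What to change.** Replace the Friedman tests, as inference, with one repeated-measures mixed model per outcome using both arms and all available patients.

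- **VAS, rest and activity separately:** model the five postoperative scores with arm, time and arm-by-time, and the pre-block score as covariate. Report the overall postoperative difference between arms and the difference at each time, with confidence intervals.
- **Heart rate and MAP:** report the arm effect over T1 to T5 as well as arm-by-time, because T1 already follows the block.
- **Within-arm time courses:** show them descriptively by arm, and state that no treatment claim rests on a within-arm P value.

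The cost is a revised Statistical Methods paragraph and somewhat more analysis work. No extra data are needed, and SPSS 25 can fit the models. The downside is a model assumption to check, because VAS scores are bounded and may be skewed. The planned non-parametric between-arm comparison could be kept as a sensitivity analysis, with the test named.
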